6.3.2 SYN023-003 Clinical Trial

Abstract	
Items	Descriptions
Title	A Phase-Ib Study on The Safety, Pharmacokinetic and Pharmacodynamic Characteristics of SYN023 in Healthy Subjects Given SYN023 by Intramuscular Injection and Subcutaneous Injection

Abstract	
Items	Descriptions
Address	inVentiv Health Inc., [name]
Number of subjects	30
Gender	Males & females
Dose groups	Intramuscular injection at 0.3 mg/kg Subcutaneous injection at 0.3 mg/kg
Formula	10 mg/mL liquid
Control	Not applicable
Volume of injection	Adjustable
Administration route	Intramuscular injection or subcutaneous injection
Administration frequency	Single dose
Follow-up period	84 days
Indicators	RVNA, PK specimens (on study days 0, 1, 3, 7, 14, 28, 35, 84): C_{max} , T_{max} , AUC_{0-48} , $AUC_{0-\infty}$, $t_{1/2}$, $\lambda_{1/2}$, V_c , CL, anti-CTB011 and anti-CTB012 antibodies, AE
Research status	Completed
Conclusion	
Efficacy/pharmacodynamics evaluation: The efficacy evaluation was performed through the pharmacodynamics evaluation of RVNA with RFFIT. The RVNA level of subjects given SYN023 in both ways reached protective level ($RVNA \geq 0.5$ IU/mL) in three days and maintained positive for more than 42 consecutive days. The concentration of RVNA in subjects given the drug by subcutaneous injection was higher than that of subjects given the drug by intramuscular injection.
 
Pharmacokinetics evaluation: The concentration levels of both CTB011 and CTB012 reached peak levels in the same time range. The concentration levels of CTB011 and CTB012 (on day 3 and day 6) given by subcutaneous injection might reach peak levels slightly faster than those of CTB011 and CTB012 given by intramuscular injection. The half-life of CTB011 was 21–23 days, while that of CTB012 was 26–29 days, which was within the typical human immunoglobulin range.
 
Anti-SYN023 antibody: Eight subjects developed anti-CTB011 antibodies before SYN023 injection. Other subjects were found of transient production of anti-CTB011 antibodies. Two subjects developed anti-CTB012 antibodies. Anti-CTB011 antibodies may be irrelevant to AEs.
 
Conclusions on safety: Eight of the 20 AEs reported headache. SYN023 at 0.3 mg/kg presented ideal pharmacodynamic and pharmacokinetic characteristics under both methods of administration. There was no death or SAE. The safety of the drug was acceptable. All AEs were mild and the AEs related to the study drug were nonspecific symptoms, such as headache and reactions at the injection sites.

6.3.3 SYN023-002 Clinical Trial

Abstract	
Items	Description
Title	A Phase II, Randomized, Blinded, Single-Dose Study on the Safety and Pharmacokinetic and Pharmacodynamic Characteristics of Rabies Vaccine and SYN023 in Healthy Subjects Receiving Rabies Vaccines.
Address	inVentiv Health Inc., [name]
Number of subjects	164
Gender	Males & females
Dose	Rabies vaccine (Imovax)+human rabies immune globulin (HRIG) Rabies vaccine (RabAvert)+human rabies immune globulin (HRIG) Rabies vaccine (Imovax)+SYN023 Rabies vaccine (RabAvert)+SYN023
Formula	10 mg/mL liquid
Control drug	HRIG
Volume of administration	To be adjusted according to weight
Administration route	Intramuscular injection
Administration frequency	Single dose
Follow-up period	112 days
Indicators	AEs, anti-CTB011 and anti-CTB012 antibody, PK specimens (at 0.1, 0.25, 0.5, 0.75, 1.0, 1.5, 2, 3, 4, 6, 12, 24 and 48 h): C_{max} , T_{max} , AUC_{0-48} , $AUC_{0-\infty}$, $t_{1/2}$, $\lambda_{1/2}$, V_c , CL.
Research status	Completed
Conclusion	
Efficacy/pharmacodynamics evaluation:
 
The generally accepted pharmacodynamic surrogate of vaccine protection level is RVNA\geq0.5 IU/mL. The RVNA levels of all subjects in the HRIG and SYN023 group reached the protection level. In the first week of post-exposure prophylaxis (PEP), the RVNA level of the SYN023 group reached the protection level faster than that of the HRIG group. In the first week, the RVNA peak concentration of the SYN023 group was higher than that of the HRIG group. Because the immune response of rabies vaccine could provide continuous immune protection, HRIG shall be used together with rabies vaccine. On the 14th day after injection of SYN023 and HRIG, the activity of RVNA of the SYN023 group reached the peak and then decreased, which was still much higher than the antibody protection level. Both HRIG and SYN023 seemed to be compatible with both licensed rabies vaccines in post exposure prophylaxis.
 
Pharmacokinetic evaluation:
 
The pharmacokinetic analysis of SYN023 components was similar to the previous two phase-I clinical studies. The concentration of CTB011 reached the peak (about 650 ng/mL) in about three days. The concentration of CTB012 reached the peak (about 920 ng/mL) in about seven days. The half-life periods of the two groups were within the

Abstract	
Items	Description
	
range of 19–23 days, which were within the typical human immunoglobulin range.
 
Anti-SYN023 antibody:
 
In the SYN023 group, 20% of the subjects developed anti-CTB011 antibodies, and about 3% of the subjects developed anti-CTB012 antibodies. The presence of the antibody had no effect on pharmacokinetics and AE.
 
Conclusions on safety:
 
There were altogether 255 AEs, in which 177 AEs were present in the SYN023 group, and 37 AEs were identified to be related to the study drug. The most common drug-related AEs were headache and reaction at the injection site. Five AEs were identified as severe, including fracture, elevated protein kinase level, and elevated troponin level. One case of severe elevation of the protein kinase level was identified to be related to SYN023 and others were related to HRIG. No death occurred in the study. One SAE was identified to be irrelevant to the study drug. The subject had an elevated troponin level before withdrawal from the study and was hospitalized for treatment, so it was identified to be SAE, which was attributed to moving house. The safety of SYN023 in healthy subjects was acceptable.
 
As a mixture of anti-rabies monoclonal antibody that could be rapidly produced, SYN023 had desirable safety, which if used together with rabies vaccine produced in the United States, could be used for rabies PEP.

6.3.4 SYN023-005 Clinical Trial

Abstract	
Items	Description
Title	A Phase I, Single-Center, Parallel and Open Bridging Clinical Trial to Evaluate The Safety, Pharmacokinetics and Pharmacodynamics of SYN023 in Healthy Subjects Given a Single Intramuscular Injection of SYN023 or Given SYN023 and Rabies Vaccine
Address	Phase I Research Center, First Hospital of Jilin University, Changchun, Jilin Province, China
Number of subjects	33
Gender	Males & females
Dose	Group A: SYN023 0.3 mg/kg Group B: SYN023 0.3 mg/kg + freeze-dried rabies vaccines for human use (Vero cells, Liaoning Cheng Da Co., Ltd)
Formula	The finished product of SYN023 is a mixture of CTB011 and CTB012 by equal quantity, containing 3.0 mg/mL active ingredients in both. The excipient buffer contains 25 mM histidine (3.879 mg/mL), 150 mM sodium chloride (8.766 mg/mL) and 0.02% polysorbate 80 (0.2 mg/mL), with a PH of 6.0. Each bottle contains 2.15 mL of SYN023, or 6.45 mg of mAb.
Control	Contrast of Group A (SYN023) and Group B (SYN023+rabies vaccine)
Volume of administration	To be adjusted according to weight of the subjects

Abstract																																																					
Items	Description																																																				
Administration route	Intramuscular injection																																																				
Administration frequency	Single dose																																																				
Follow-up period	85 days, including 8-day in hospital observation after administration.																																																				
Indicators	Safety, pharmacokinetics, anti-drug antibody																																																				
Research status	Completed																																																				

Parameters	Statistics			Group A (SYN023)		Group B (SYN023+rabies vaccine)																																															
		CTB011	CTB012	CTB011	CTB012																																																
AUC _{0-t} (h*ng/mL)	Mean (SD) (91433.40)	690713.69 (129362.11)	468955.56 (138435.66)	779026.35 (156758.07)	487821.52 (141633.10)																																																
AUC _{0-∞} (h*ng/mL)	Mean (SD) (111041.26)	774711.08 (122741.74)	507604.98 (176114.53)	872700.78 (141633.10)	565246.72 (132.85)																																																
C _{max} (ng/mL)	Mean (SD) (145.74)	730.48 (186.73)	614.83 (230.46)	784.77 (132.85)	613.17 (48.00,335.53)																																																
T _{max} (h)	Median (Min, Max) (72.00,336.67)	252.33 (120.00,336.67)	168.00 (48.00,335.53)	167.50 (48.00,335.53)	167.50 (48.00,335.53)																																																
t _{1/2} (h)	Mean (SD) (85.87)	572.14 (34.19)	333.23 (114.27)	577.40 (424.12)	114.27 (152.69)																																																
CL/f(mL/h)	Mean (SD) (4.82)	24.55 (12.52)	39.04 (5.29)	22.96 (35.78)	5.29 (8.28)																																																
Kel(1/h)	Mean (SD) (2.29×10 ⁻⁴)	1.24×10 ⁻³ (2.13×10 ⁻⁴)	2.10×10 ⁻³ (2.40×10 ⁻⁴)	1.24×10 ⁻³ (5.34×10 ⁻⁴)	1.80×10 ⁻³ (48.00,335.53)																																																

Abstract	
Items	Description
	
Safety:
 
Both SYN023 (0.3mg/kg) alone and SYN023 (0.3mg/kg) + rabies vaccine PEP were quite safe for the Chinese subjects. No SAE, or AE of Grade-3 (CTCAE5.0) or above that were related to the study drug occurred. No death occurred.
 
Five subjects (62.5%) in Group A reported fourteen AEs, and AEs with a relatively high incidence (incidence $\geq 25\%$) were elevated alanine aminotransferase, elevated aspartate aminotransferase, elevated blood creatinine, and hypertriglyceridemia. Three subjects (37.5%) in Group A reported four AEs that were related to the study drug, including elevated alanine aminotransferase, elevated aspartate aminotransferase, hypertriglyceridemia and anemia, each with an incidence of 12.5%. One subject (12.5%) experienced two Grade-3 AEs (nephrolithiasis and hydronephrosis) due to recurrence of kidney stones, which was identified to be irrelevant to the study drug, and recovered after lithotripsy treatment, and then dropped out of the test; two subjects (25.0%) experienced three Grade-2 AEs, including one case of hypertriglyceridemia that might be related to the drug, which was an unintended adverse reaction; the remaining AEs were Grade-1 events.
 
21 subjects (87.5%) in Group B reported 76 AEs, and AEs with a relatively high incidence (incidence $\geq 25\%$) was decreased white blood cell count. 13 subjects (54.2%) in Group B reported 30 AEs that were related to the study drug, and AEs with a relatively high incidence (incidence $\geq 12.5\%$) were decreased neutrophil count, decreased leukocyte count and back pains. Two subjects (8.3%) experienced two Grade-3 or higher-grade AEs (hypertriglyceridemia and increased creatine phosphokinase), which were identified to be irrelevant to the study drug, and recovered without any treatment; seven subjects (29.2%) experienced 15 Grade-2 AEs; the remaining events were Grade-1 AEs; four subjects (16.7%) reported six unintended adverse reactions.
 
The incidence of AEs in Group B was higher than that in Group A, which might be related to the administration of the rabies vaccine.
 
No death occurred in the Chinese and American studies; one SAE occurred in the American study, which was not related to the study drug based on evaluation, and no SAE occurred in the Chinese study. There were four and three Grade-3 and higher-grade AEs in the Chinese study and American study, respectively, which were identified to be irrelevant to the study drug; there were no anemia, acute injection reactions and other unusual AEs. In terms of drug-related AEs, no headache, pains at the injection site and other reactions that were common in the American study were reported in the Chinese study, but the Chinese study showed higher incidences of decreased neutrophil count and leukocyte count than the American study.


6.3.5 SYN023-004 Clinical Trial

This study is a randomized blinded phase-IIb clinical trial on the effect of rabies vaccine+SYN023 and rabies vaccine+HRIG in people aged 18 years and over and exposed to rabies to different degrees. Intending to recruit 448 subjects, this study has completed the enrollment and patients are in the follow-up status.

7. STUDY ENDPOINTS

7.1 Primary Endpoints

- GMC of RVNA on Day 8 after administration.
- The incidence and survival rate of rabies in subjects within 99 days and 1 year after administration.

7.2 Secondary Endpoints

- The protection level (percentage of RVNA concentration ≥ 0.5 IU/mL) and GMC of RVNA on Study Days 4, 8, 15, 43, 99, 183, and 365 after administration;
- AUEC of RVNA GMC from Study Day 1 to Day 15 after administration (AUEC₁₋₁₅);

7.3 Safety Endpoints

- All AEs regardless of related or un-related with IMPs within 30 minutes post administration will be collected ;
- Injection/vaccination sites (local)'s AE and (Systemic) adverse events occurring at sites other than the injection/vaccination sites within 1~8 days post administration;
- All AEs related or unrelated to the study drug occurring within 1~43 days post administration;
- Grade 3 or higher AEs occurring within 1~43 days post administration;
- All SAEs related or unrelated to the study drug occurring during the study;
- Pregnancy events occurring within 6 months after administration (pregnancy status and outcome);
- AEs/SAEs leading to withdrawal.

8. TRIAL DESIGN

8.1 Overall Design

A randomized, blinded and controlled design is adopted in this clinical trial.

8.1.1 Sample Size and Grouping

In this study, 1000 subjects aged 18 and over who had Grade 3 exposure to rabies virus were intended to be enrolled, and randomly assigned to the experimental group and the control group (3:1). Both groups were immunized according to PEP procedures for rabies. Specific sample size and distribution of rabies vaccines are described as follows:

Group	Sample Size	Study Drug	Administration Method & Dosage	Time of Injection
Experimental Group	750	SYN023	0.3 mg/kg, wound infiltration injection*	Study Day 1

		Rabies vaccine for humans	0.5 mL, intramuscular injection into the deltoid muscle	Study Days 1, 4, 8, 15, 29 (Essen Scheme)
Control Group	250	HRIG	20 IU/kg, wound infiltration injection*	Day 1
		Rabies vaccine for humans	0.5 mL, intramuscular injection into the deltoid muscle	Study Days 1, 4, 8, 15, 29 (Essen Scheme)

*: If the drug isn't used up after infiltration injection for all wounds, the remaining amount should be injected into the muscles far away from the vaccine injection sites (if a wound is located above the waist, the remaining amount should be injected into the back muscles on the side where the wound is located; if a wound is located below the waist, the remaining amount should be injected into the lateral muscles in the middle thigh on the side where the wound is located).

8.1.2 Study Drug's Administration

All subjects were given SYN023 or HRIG by infiltration injection at the wound site, and the first dose of freeze-dried rabies vaccine for human use (Vero cells) was intramuscularly injected at the deltoid of upper arm on Study Day 1, followed by dosing on Study Days 4, 8, 15 and 29.

Note: If the drug isn't used up after infiltration injection for all wounds, the remaining amount should be injected into the muscles far away from the vaccine injection sites (if a wound is located above the waist, the remaining amount should be injected into the back muscles on the side where the wound is located; if a wound is located below the waist, the remaining amount should be injected into the lateral muscles in the middle thigh on the side where the wound is located).

8.1.3 Efficacy Evaluations

3.0 mL of venous blood should be sampled 8 times from each subject prior to administration and on Days 4, 8, 15, 43, 99, 183, and 365 after administration respectively for the evaluation of RVNA levels. Relevant information should be collected from the subjects through follow-ups, such as occurrence of rabies and survival conditions.

RVNA should be tested for all blood samples through rapid fluorescence focus inhibition test (RFFIT).

8.1.4 Safety Evaluations

All solicited adverse events should be collected within 1~8 days post administration; all adverse events occurring within 1~43 days post administration should be collected, and all pregnant events occurring within 6 months post administration and all SAE during the study period should be collected.

8.2 Randomization & Blinding Methods

8.2.1 Randomization

In this trial, the block randomization method is adopted. After providing informed

consents, the enrolled subjects should be randomly assigned to the SYN023 group (the study drug group) or the HRIG group (the control drug group) at a ratio of 3:1, with the site as a stratification factor. Each subject should be injected with the corresponding drug based on the same procedures and then with the rabies vaccine.

In this study, a web based central randomization system is used to carry out random grouping for all subjects. The randomized blinded codes refer to the list of randomly assigned subjects and the list of randomly assigned study drugs (blinded codes) generated by an independent non-blinded randomization statistician from the statistical agency with the SAS software (version 9.4 or above) according to the protocol. The list of randomly assigned subjects contains the site number, random number (namely study number) and the study drug group corresponding to the random ID number of each subject (the study drugs herein generally refer to the study drug SYN023 and the control drug HRIG). The list of randomly assigned study drugs contains the random drug number and the study drug corresponding to the random drug number. Non-blinded database designers should upload the list of randomly assigned subjects and the list of randomly assigned study drugs (blinded codes) to the IWRS and complete the automatic interfacing setup for the interactive net response system, IWRS, and the EDC system, the Medidata Blance and Rave. After system setup, the investigators or other qualified personnel designated by the investigators should create subject information in the EDC and assign a random number for each eligible subject with the IWRS based on the study site after confirming that the subject's eligibility for enrollment. After the completion of random assignment of the subjects, the system will automatically assign the drug number in each visit for drug administration according to the corresponding drug group. Relevant investigators on each study site should provide treatment to each subject in accordance with the drug number assigned by the system. The entire randomization process should be completed in the EDC and IWRS, and the authority of users is strictly controlled in both systems to ensure the maintenance of blindness during the study. If a randomly assigned subject withdraws from/drops out of the clinical trial for any reason, regardless of whether the subject has been given any study drug, his/her random number cannot be reassigned to another subject.

8.2.2 Blinding

In order to reduce/avoid bias in operations, a double-blinded design will be adopted in this study. The randomization statistician and other personnel responsible for blinding should perform blinding for the drugs, in which the drugs used in this study should be packaged with same boxes and sealed up, in order to make sure that there is no difference in the packages of the study drug and the control drug. Therefore, one cannot figure out the drug given to any subject based on the package only, thereby ensuring blindness of the drugs used in the study. In

this study, personnel responsible for non-blinded drug injection and drug administration are arranged. Except for these personnel, anyone cannot unseal and get access to any study drug, and any subject cannot observe the size of the drug vial. In addition, the syringes should be appropriately masked so as to ensure that a subject cannot observe the color and dosage of the study drug, and thus cannot figure out the drug given to him/her based on its color or the size or appearance of the vial. In this way, the blindness of the drugs used in this study can be ensured.

Blinding for drugs should be carried out by the randomization statistician and other personnel who will not be involved in the implementation of the clinical trial. Under the guidance of the randomization statistician, blinding operators attach the printed labels with numbers to the outer packages of the study drug/control drug according to the blinded codes and seal the packages with sealing stickers.

After the completion of blinding for drugs, the blinded codes shall be sealed and kept by the randomization statistician. The entire blinding process must be documented. The personnel responsible for blinding must not participate in other relevant works during this clinical trial, and must not disclose the blinded codes to any person participating in this clinical trial.

8.2.3 Maintenance of Blindness

The dosage of the study drug is different from that of the control drug (the dosage of the study drug is 0.1 mL/kg; the dosage of the control drug is 0.2 mL/kg), the "blindness" in this trial applies to the subjects, observers, investigators and laboratory testers.

- 1) The package must be kept sealing before use; otherwise the drug inside the package will be deemed to be used drug.
- 2) The personnel responsible for drug injection should prepare drugs prior to drug injection. Other personnel are not allowed to be present when these works are being done. After the completion of drug preparation, the subjects should be guided by specific triage staff to the vaccination rooms one by one for vaccination. One vaccination room can only accommodate one subject for drug/vaccine injection each time, and the syringe should be appropriately masked to ensure that the subject cannot observe any identification information of drug and vaccine given to him/her (such as outer package, drug color, etc.);
- 3) The personnel responsible for drug preparation should put the empty vials/boxes back to the original packages, check them in a timely manner after the completion of work every day, and seal them up for storage together with the drug administrator. After a study site is closed and the Sponsor's authorization is obtained, the study site should transfer these packages to the provider of medical waste disposal services or the

Sponsor for destruction, and destruction record should be kept;

- 4) The inspection and quality control related to drug management and drug injection should be performed by non-blinded CRAs and quality controllers;
- 5) The blood samples collected during the study can only be identified by the study number.

8.2.4 Emergency Unblinding

Unless it is necessary to meet medical needs, unblinding of the treatment for subjects isn't allowed without the consent of the Sponsor and the investigators and should be with the recommendation of DSMB. In case of any serious adverse event that requires emergency treatment during the study, emergency unblinding can be performed through IWRS if the investigator believe that it is necessary to learn about the drug group and it is beneficial for the handling of the adverse event. The investigator must enter relevant information into the IWRS, such as the reason(s) for emergency unblinding, and reconfirm the necessity of unblinding prior to emergency unblinding. If possible, every effort should be made to notify the principal investigator, CRA, and relevant personnel of the Sponsor of such unblinding before emergency unblinding, and the specific grouping information of the subject can be obtained only with the approvals of the Sponsor and the principal investigator. If the Sponsor cannot be reached before emergency unblinding, it is necessary to contact the Sponsor, the principal investigator, and the CRA within 24 hours after emergency unblinding. The subject requiring emergency unblinding will be deemed as a drop-out case.

Refer to the separate operation manual for the specific emergency unblinding procedures. Please also refer to the DSMB 14.3 chapter.

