14.8 Individual Emergency Unblinding

If any serious adverse event occurs during the study period, individual emergency unblinding should be performed only if the subjects involved require medical emergency or treatment and the information of the product studied is critical to the clinical treatment of the said subjects. Investigators should complete the recordation of the unblinding process and promptly report it to the Sponsor and the Institutional Review Board.

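### Protocol 8.2.4 contradicts itself on whether emergency unblinding needs prior approval when the Sponsor can be reached

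*Protocol*

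**What the plan says.** Protocol Section 8.2.4 deals with emergency unblinding in this order:

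- **General rule and exemption.** "Unless it is necessary to meet medical needs, unblinding of the treatment for subjects isn't allowed without the consent of the Sponsor". Consent from the investigators is named as well, and a DSMB recommendation is also expected.
- **Who decides in an emergency.** For a serious adverse event needing emergency treatment, "emergency unblinding can be performed through IWRS if the investigator believe that it is necessary to learn about the drug group" and that knowing it would help in handling the event. The investigator enters the reason in IWRS and reconfirms the need.
- **Prior notification.** "If possible, every effort should be made to notify the principal investigator, CRA, and relevant personnel of the Sponsor of such unblinding before emergency unblinding".
- **Approval.** The same sentence continues: "the specific grouping information of the subject can be obtained only with the approvals of the Sponsor and the principal investigator".
- **Fallback, with contact following the unblinding.** "If the Sponsor cannot be reached before emergency unblinding, it is necessary to contact the Sponsor, the principal investigator, and the CRA within 24 hours".
- **Detail elsewhere.** "Refer to the separate operation manual for the specific emergency unblinding procedures".

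Protocol Section 14.8 covers the same act. It sets a clinical condition, tied to the subject's treatment: "individual emergency unblinding should be performed only if the subjects involved require medical emergency or treatment and the information of the product studied is critical". It then sets a duty afterwards: "Investigators should complete the recordation of the unblinding process and promptly report it to the Sponsor and the Institutional Review Board". It mentions no prior approval.

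**The concern.** An investigator treating a serious adverse event needs one clear answer to one question: may I open the code now, or must I wait for someone's agreement? The opening of 8.2.4 and the whole of 14.8 say that the investigator may proceed. The approval clause says that the allocation is available only once two other parties have agreed.

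Followed literally, the clause could hold back information in exactly the circumstances that 14.8 describes, where knowing the product is critical to treatment. The principal investigator need not be at the bedside. Under Section 4.2 the provincial CDC designates that person, while subjects are treated at five city and county CDC sites.

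What is at stake is subject safety in a rare event. The clause does not enter any estimate or test.

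**Working it through.** No arithmetic applies beyond counting the approvals that each rule names, so the check is to set the rules side by side.

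| Text | Who decides | Prior approvals named | Duty to inform |
|---|---|---|---|
| 8.2.4, opening sentences | Investigator, through IWRS | 0 where there is medical need | Reason entered in IWRS |
| 8.2.4, approval clause | Sponsor and principal investigator | 2 | Prior notification where possible |
| 8.2.4, fallback | Investigator, when the Sponsor is unreachable | 0 | Contact within 24 hours afterwards |
| 14.8 | Investigator, if the clinical condition is met | 0 | Record, and report promptly to the Sponsor and IRB |

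**Step 1: Sponsor cannot be reached.** The fallback allows unblinding first and contact afterwards. This agrees with the opening sentences and with 14.8. There is no practical conflict.

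**Step 2: Sponsor can be reached.** The fallback is not triggered. The opening exemption points to the investigator's own decision, and the approval clause points to two approvals. Both concern access to the same subject's allocation in the same emergency, and 8.2.4 does not say which prevails. The fallback depends on the Sponsor alone. It therefore does not address a Sponsor who has been contacted but has not yet answered, or a Sponsor who is reached while the principal investigator is not.

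**Step 3: Does other text settle it?**

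- Section 14.8 needs no approval, but it does not say that it overrides 8.2.4, nor the reverse.
- Section 13.7 on the DSMB contains no unblinding rule and leaves working details to a charter.
- Section 8.2.5 covers the planned unblinding after Day 99.
- Section 9.7 covers early unblinding to decide whether the trial continues. Neither this nor 8.2.5 governs the treatment of one subject.
- SAP Sections 1.3.2.1 to 1.3.2.3 describe randomisation and blinding and give no emergency rule.

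Nothing in the protocol or SAP resolves Step 2.

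**The case against.** The strongest reply is that 8.2.4 can be read as a coherent sequence. Medical need is exempt at the outset, and the exemption does not depend on who can be reached. The investigator decides through IWRS. The sentence holding the approval clause begins conditionally, so both notification and agreement could be best-effort. Section 14.8 is consistent with that sequence. This reading is grammatically available, and it means the text is not shown to block unblinding. It is weak, however: *only* is mandatory language, and a fallback confined to an unreachable Sponsor implies that approval is otherwise expected. If the reading is what was meant, the same one-clause change makes it plain.

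Second, the operation manual may already give the right procedure. That cannot be checked here. If it does, the protocol wording should agree with it.

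Third, the clinical consequence is limited, and this stands. Study drug is given on Day 1 only, so no later study-drug dose depends on the code. On-site first aid and epinephrine (Section 10.7) and the green-channel hospital arrangements (Section 14.1) do not depend on it either, and the documents name no arm-specific treatment. This is why the point is minor.

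It might also be said that the unblinded injection staff already know the arm. They are not a sanctioned route: SAP Section 1.3.2.3 has them sign a non-disclosure agreement that covers the investigators.

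A reader might infer that the protocol forbids emergency unblinding without approval, or that subjects would in practice be delayed. The documents support neither. The first ignores the medical-need exemption and the 24-hour fallback. The second would require knowing the manual's procedure, whether IWRS is set to wait for approvals, and how often such emergencies arise, none of which is given.

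**Conclusion.** The inconsistency is real and confined to a medical emergency in which the Sponsor can be reached. In that situation one part of 8.2.4 leaves the decision to the investigator and another names two required approvals, while 14.8 names none.

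It is a minor subject-safety correction. It has no effect on estimates, type I error or power, and no frequency of delay can be derived from the documents.

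Confidence is medium. The conclusion rests on reading *only* as mandatory and on the protocol and SAP alone; the operation manual could show that practice is already sound. Even then the protocol should be corrected, because a manual that required no approval would contradict the approval clause as it stands.

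**What to change.** In Section 8.2.4, replace the approval clause with:

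> The Sponsor and principal investigator are notified beforehand where possible, but their approval is not required and must not delay emergency unblinding; if not notified beforehand, they and the CRA are contacted within 24 hours afterwards.

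Add a cross-reference to this sentence in Section 14.8. Check that the operation manual says the same, and remove any IWRS setting that makes disclosure wait for approvals.

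Keep the other safeguards as they are: the clinical threshold and reason entry in 8.2.4, the prompt report to the IRB in 14.8, and the consent and DSMB conditions for unblinding that is not a medical emergency.

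The cost is one clause, one cross-reference, and a check of the manual and IWRS. Under Section 8.3 every amendment goes to the IRB, and one that may affect subject safety needs IRB approval, normally before it is put into effect. Sample size and analysis do not change.
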